2.2 Secondary

1. To assess the correlation between targeted molecular uptake of ⁶⁸Ga-PSMA PET in thyroid cancer compared to areas identified as tumor by radioiodine uptake (in well-differentiated cancers) or ¹⁸F-FDG uptake (in poorly differentiated and/or radioiodine-negative cancers).
2. To determine and compare the sensitivity and specificity of ⁶⁸Ga-PSMA PET to ¹⁸F-FDG PET and/or radioiodine scintigraphy

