5.1.2 Study Period

5.1.2.1 ^{68}Ga -PSMA PET/MRI

Subjects will be injected with ^{68}Ga -PSMA [REDACTED] and, if needed, transported to the imaging site. After the biodistribution period (50 to 80 minutes after radiotracer injection), coverage for the scan will extend from the patient's vertex through the thighs.

A standard neck MRI will be performed concurrently with the PET/MRI. This MRI will be performed without and with gadolinium contrast intravenously. Gadolinium contrast will not be administered if the patient cannot receive contrast based on Radiology Department guidelines. A whole body (vertex to toes) MRI (PET/MRI) will be performed for attenuation correction and anatomic localization. Patients may be given lorazepam as needed, to keep them from feeling anxious during the scan. The entire imaging study will take roughly 60 minutes. Imaging will be performed at [REDACTED] UCSF [REDACTED].

No formal report of the findings from imaging studies will be created. Each study will be reviewed by a board-certified nuclear medicine physician and a board-certified radiologist within two working days of the completion of the study. ^{68}Ga -PSMA PET results will not be used for clinical care. If any unexpected findings are visualized, these will be reported to the treating health care provider, who will then contact the patient if additional work-up needs to be performed.

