6.7 Image Processing and Analysis

A trained nuclear medicine physician blinded to results of tissue analysis will evaluate the reconstructed PET, MRI, and fused PET/MR images using a PET volume computer-assisted reading software package. A positive lesion on gallium PSMA-11 PET will be defined as a focus of activity with at least 1.5 times higher SUV compared with mediastinal blood pool that is not attributable to other etiologies of tracer distribution (e.g. excretion) or above liver background. A volume of interest (VOI) will be semiautomatically placed around each lesion, and the calculated maximum standard uptake value (SUV_{max}) will be recorded for each lesion. Adjusted SUV_{max} data will then be averaged across all lesions within a given patient ($SUV_{max-avg}$) if needed. In order to avoid clustering effects, analysis will be limited to the five largest lesions per study.

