6.10 Analyses Plans

The number of ^{68}Ga PSMA-11 PET-positive lesions and number of overall thyroid cancer lesions detected by standard staging scans will be descriptively reported for each patient and correlated with the lesions observed in standard MRI imaging. In addition, the mean, range, and standard deviation of SUV_{max} (across all visualized lesions per patient) and $SUV_{max-avg}$ (across all patients in the study cohort) will be descriptively reported.

For each lesion detected on ^{18}F -FDG PET or radioiodine scintigraphy (^{131}I), the presence or absence of ^{68}Ga -PSMA-11 uptake will be reviewed and tabulated. Presence on either ^{131}I and ^{18}F -FDG will be considered true positive disease. If additional lesions are detected on ^{68}Ga -PSMA-11 as compared to ^{18}F -FDG or ^{131}I , the lesions will be characterized as either true or false positives in comparison to the appearance of the lesion on conventional imaging (thyroid ultrasound, CT and MRI). The gold standard for an individual lesion will be FDG or ^{131}I , if the individual lesion is positive on either imaging study. If the lesions are not seen on either FDG or ^{131}I , then consensus reading of conventional imaging will be performed to determine true and

false positive lesions. The total number of lesions detected using each technique will be compared, and this data will be used to determine the sensitivity and specificity of ^{68}Ga -PSMA-11 for the detection of disease. If a larger number of lesions are detected using ^{68}Ga -PSMA-11 compared to ^{18}F -FDG PET and ^{131}I , this provides promising preliminary data, which can be used to justify study in a larger clinical trial.

The patient cohort will be dichotomized by thyroglobulin level. The mean $\text{SUV}_{\text{max-avg}}$ between dichotomized subgroups will be compared using the non-parametric Mann-Whitney U test. The correlation between SUV_{max} on ^{68}Ga -PSMA PET and thyroglobulin level as a continuous variable will also be determined using Pearson correlation method.

In those patients with adequate archival FFPE the correlation between SUV_{max} on ^{68}Ga -PSMA PET and tumor PSMA expression will be explored using Pearson correlation method.

7 Study Management

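### Section 6.10 makes FDG and 131I their own gold standard while PSMA-only lesions are adjudicated, so comparator specificity is 100% by construction and the specificity comparison is settled in advance

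*Combined protocol and SAP*

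**What the plan says.** Secondary objective 2 (section 2.2) is "To determine and compare the sensitivity and specificity of" PSMA PET against FDG PET and/or radioiodine scintigraphy.

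Section 6.10 supplies the reference standard, and it depends on which tracer saw the lesion:

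- **Positive on FDG or 131I.** "Presence on either ^{131}I and ^{18}F -FDG will be considered true positive disease". The same section adds: "The gold standard for an individual lesion will be FDG or ^{131}I , if the individual lesion is positive on either imaging study".
- **Positive on PSMA only.** "If the lesions are not seen on either FDG or ^{131}I , then consensus reading of conventional imaging will be performed", and "the lesions will be characterized as either true or false positives in comparison to the appearance of the lesion on conventional imaging". Ultrasound, CT and MRI are the named modalities. Only two outcomes exist, true or false.

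No section sends a lesion that is FDG- or 131I-positive but PSMA-negative to conventional imaging, histology or follow-up. The MRI correlation at the start of 6.10 is descriptive. Archival tissue (5.1.3, 6.10) is used only to relate SUVmax to PSMA expression. Section 6.7 gives a positivity threshold for PSMA and excludes uptake with another explanation, such as excretion. No corresponding criterion is written for FDG or 131I.

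**The concern.** A test that serves as its own reference cannot be wrong when it is positive. Under 6.10 the comparators can miss disease but cannot overcall it, whereas PSMA can do both. Half of the planned accuracy comparison, the specificity half, therefore has one arm fixed before any patient is scanned.

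The rule also reaches sensitivity. If a reader calls a focus on FDG or 131I a lesion and it is in fact benign, it enters the disease denominator. If PSMA does not take it up, PSMA is charged with a miss for being right. Section 6.10 says that a larger lesion count on PSMA would help to justify a larger trial, and section 6.8 bases the sample size on a sensitivity difference, so these are the figures that readers will carry forward.

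A second gap concerns PSMA-only lesions that conventional imaging cannot settle. Standard scans are done as clinically indicated and may be up to about 360 days old (5.1.1). The contrast MRI is of the neck, and the whole-body MRI "will be performed for attenuation correction and anatomic localization" (5.1.2). The plan does not say how a focus without adequate imaging is to be called.

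**Working it through.** **Plan's own figure.** Section 6.8 gives 20 patients per comparator, power 0.87, one-sided 0.05, sensitivities 0.65 and 0.90. An exact one-sample binomial test with n = 20 that rejects at 17 or more successes has alpha 0.044 under 0.65 and power 0.867 under 0.90. The stated figure reproduces, with 0.65 treated as a known rate. The present point does not alter that calculation; it only borrows the two sensitivities.

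**Specificity.** Comparator specificity = TN / (TN + FP). Under 6.10 every comparator-positive lesion is disease, so FP = 0 and specificity = TN / TN = 100% for any non-zero count of true negatives. No data are needed.

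**Sensitivity, as an illustration.** Assumptions: 100 true lesions; the two tracers detect independently at 0.65 and 0.90; every PSMA-only true lesion is confirmed on conventional imaging; a share f of comparator-positive lesions is benign and PSMA-negative. The documents give no value for f, so a range is shown.

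- Seen on both: 100 × 0.65 × 0.90 = 58.5
- Comparator only, true: 100 × 0.65 × 0.10 = 6.5
- PSMA only, true: 100 × 0.35 × 0.90 = 31.5
- Seen on neither: 100 × 0.35 × 0.10 = 3.5, never counted
- Benign comparator lesions: B = 65 × f / (1 − f)

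Lesions counted as disease: D = 58.5 + 6.5 + 31.5 + B = 96.5 + B. Apparent PSMA sensitivity = 90 / D. Apparent comparator sensitivity = (65 + B) / D.

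| f | B | D | PSMA | Comparator | Gap (points) |
|---|---|---|---|---|---|
| 0 | 0 | 96.5 | 0.933 | 0.674 | 26 |
| 5% | 3.42 | 99.92 | 0.901 | 0.685 | 22 |
| 10% | 7.22 | 103.72 | 0.868 | 0.696 | 17 |
| 20% | 16.25 | 112.75 | 0.798 | 0.721 | 8 |

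If comparator-only lesions were adjudicated too and the benign ones removed, the result would be 0.933 vs 0.674 at every f.

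**Direction.** Now let all the benign comparator lesions be PSMA-positive instead. At f = 10%, apparent PSMA sensitivity = (90 + 7.22) / 103.72 = 0.937, slightly above the 0.933 at f = 0. The rule then credits PSMA with finding lesions that are not disease.

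**Unverifiable PSMA-only lesions.** If u of N PSMA-only lesions have no adequate conventional image, the fraction called true can differ by u/N according to how they are called. The plan leaves this choice open.

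**The case against.** Several stronger readings are tempting, and the documents do not support them.

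- *A reader might infer that every reactive node or thyroid remnant with uptake becomes disease.* Section 2.2 speaks of areas identified as tumor and 6.10 of thyroid cancer lesions, so a reader may discount recognised benign uptake before calling a lesion. The absence of a written criterion for standard-of-care scans does not mean that all their uptake counts. What remains is the unrecognised misread.
- *That PSMA sensitivity is measured as 0.90 × (1 − f).* That takes comparator-positive lesions as the whole denominator. Section 6.10 also counts confirmed PSMA-only lesions, which gives the values in the table.
- *That the bias always runs against PSMA.* At f = 0 the rule overstates PSMA (0.933 against 0.90), because lesions missed by both tracers are never counted. At 5% it is about neutral. Benign foci positive on both tracers favour PSMA, and section 1.2 notes that PSMA is expressed in various normal tissues.
- *That missing imaging turns into PSMA errors.* Section 6.10 does not say so; the call is undefined. Every patient also has a same-session whole-body MRI, which 6.7 has evaluated, and 6.10 lists MRI as conventional imaging.
- *That comparator sensitivity is fixed.* It is not: each confirmed PSMA-only lesion is a comparator miss.

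It is also fair to say that this is a single-center feasibility pilot, that the comparison is secondary, and that PSMA results do not guide care. That lowers the stakes. It does not answer the specificity point, which follows from the stated rule alone.

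**Conclusion.** The point holds in a limited form. As written, 6.10 sets comparator false positives to zero and any comparator specificity to 100%, so the specificity half of objective 2 cannot be informative. This rests on the text and on no assumption.

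The effect on sensitivity is conditional. If the benign comparator lesions are PSMA-negative, the apparent advantage of PSMA shrinks from 26 points at f = 0 to 17 at 10% and 8 at 20%; if they are PSMA-positive, apparent PSMA sensitivity rises slightly. These figures depend on the assumed f, on independent detection and on full confirmation of PSMA-only true lesions. They show how far the rule can move the result, not how far it will. The handling of unverifiable PSMA-only lesions is a gap in definition, not a built-in penalty.

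The plan should be amended, since the remedy is small, but the point does not undermine the feasibility aim.

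**What to change.** In section 6.10:

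1. Keep the present rule as one analysis.
2. Add an analysis in which FDG/131I-only lesions go to the same planned consensus reading of conventional imaging, including the study MRI, as PSMA-only lesions. Use the planned readers, masked where feasible to which tracer was positive.
3. Allow three outcomes: confirmed, not disease, unverified. Call a lesion unverified when no adequate conventional image exists, or when treatment or a long interval between scans could explain the discordance. The second condition matters because section 3.3.1 allows the comparator scan to precede PSMA PET by up to 360 days, and a treated or resolved lesion should not be labelled as not disease.
4. Report sensitivity and false-positive counts for PSMA and for each comparator three ways: unverified lesions excluded, all counted as disease, and all counted as not disease.
5. State that comparator specificity is not estimable under the present rule, and that lesions positive on both tracers remain unadjudicated unless they are also read.

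The cost is protocol wording and somewhat more reading work, with no new scan and no requirement for new readers. Masking may be incomplete, because the study readers also see the PET images. The accuracy figures may come out wider or less favourable.

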3.3.1 Inclusion Criteria

1. History of thyroid cancer
2. Whole body ^{18}F -FDG PET/CT, I-123 or I-131 scintigraphy within the past 360 days of the scheduled ^{68}Ga -PSMA PET demonstrating uptake.
3. Age 18 years or older at the time of study entry
4. Creatinine $\leq 3.0 \text{ mg/dL}$
5. Ability to understand a written informed consent document, and the willingness to sign it

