5.1 Dosage and Administration

⁶⁸Ga-PSMA will be administered on an outpatient basis. It will be administered at a single time point, intravenously, prior to PET imaging. The one-time nominal injected dose will be approved by the UCSF Radiation Safety Committee (RSC) and will be 3 to 7 mCi.. A simultaneous whole body PET/MRI will be used for attenuation correction and anatomic localization of ⁶⁸Ga-PSMA uptake and SUV calculation. ⁶⁸Ga-PSMA is currently in use at UCSF under an IND in prostate cancer with over 300 patients injected and no significant adverse events. Additionally, this radiotracer has been used safely in Europe with over a thousand studies performed without a significant adverse event. For this protocol, ⁶⁸Ga-PSMA will cross reference the currently active IND for prostate cancer that is being used at UCSF. A neck MRI with gadolinium (MR) will be performed at the time of the PET imaging. Gadolinium contrast will not be administered if the patient cannot receive contrast based on Radiology Department guidelines.

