5.1.1 Screening Assessments

The Screening procedures and assessments must be completed within 28 days of the Day 1 Visit, unless otherwise noted.

A written, signed, informed consent form (ICF) and a Health Insurance Portability and Accountability Act (HIPAA) authorization must be obtained before any study-specific assessments are initiated. A copy of the signed ICF will be given to the subject and a copy will be filed in the medical record. The original will be kept on file with the study records.

All patients who are consented will be registered in OnCore®, the UCSF Helen Diller Family Comprehensive Cancer Center Clinical Trial Management System (CTMS). The system is password protected and meets HIPAA requirements.

In addition to OnCore, REDCap will be used to collect data for this study. REDCap is a secure, HIPAA-compliant, web-based system.

- Complete medical history
- Baseline standard staging diagnostic exams may be done approximately 360 days before PSMA PET as clinically indicated. Patients may receive staging scans and ⁶⁸Ga-PSMA PET imaging on the same day if the patient meets eligibility criteria for the study as assessed by the Principal Investigator prior to the completion of the scan.
- Pregnancy testing in women of childbearing potential (WOCBP)
- Creatinine
- Thyroglobulin

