5.1.4 Optional repeat scan

An optional follow up ^{68}Ga -PSMA PET study may be obtained between 2 and 6 months after completion of the first PET. Optional PET will be performed to determine any interval changes in PSMA uptake and compare them to clinical changes including thyroglobulin. The potential for follow-up examination will be discussed and consented for during the original consent process. The study team will contact the patient after completion of the PET about repeat imaging. Sections 5.1.2 and 5.1.3 will be followed during the follow-up imaging.

A maximum number of two ^{68}Ga -PSMA studies (initial and optional follow up) will be performed under this protocol.

Period/ Procedure	Screening	Imaging	Optional Imaging
Study Day/Visit Day	-28 to 1	D1	2-6 months after 1st ⁶⁸Ga- PSMA PET
Informed consent	X		
AE assessment			X ²
Concomitant medications	X	X	X ²
Clinical procedures			
Medical history including prior/concomitant systemic therapies for thyroid cancer	X		
Laboratory procedures			
Creatinine	X		
Thyroglobulin	X		
Pregnancy test (HCG) (WOCBP only)	X		
Imaging procedures			
Standard diagnostic scans as clinically indicated ¹	X ¹		
⁶⁸ Ga-PSMA-11 administration		X	X ²
Whole body PET/MRI		X	X ²

1. Standard of care PET scan may be done up to 360 days before PSMA PET. Patients may receive staging scans and 68Ga-PSMA PET imaging on the same day if the patient meets eligibility criteria for the study as assessed by the Principal Investigator prior to the completion of the scan.
2. Only required if patient agrees to optional follow-up 68Ga-PSMA PET.

6 Reporting and Documentation of Results

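### Section 6.10 does not separate lesions that appeared or disappeared between the comparator scan and PSMA PET from lesions a tracer missed, and the net bias is unknown

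*Combined protocol and SAP*

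**What the plan says.** **Timing.** Section 3.3.1 (criterion 2) requires FDG PET/CT or radioiodine "scintigraphy within the past 360 days of the scheduled" PSMA PET, with uptake shown. Section 5.1.1 says "Baseline standard staging diagnostic exams may be done approximately 360 days before PSMA PET as clinically indicated", and the schedule footnote in 5.1.4 says "Standard of care PET scan may be done up to 360 days before PSMA PET". Same-day scanning is allowed, not required: section 5.1.1 permits staging scans and "PET imaging on the same day if the patient meets eligibility criteria for the study". Section 6.8 gives the 360 days without a direction, but the eligibility criterion settles it. An optional second scan is allowed: a "PET study may be obtained between 2 and 6 months after completion of the first PET". Section 6.10 does not say whether it is kept out of the lesion comparison.

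**Scoring.** In section 6.10 any lesion positive on FDG or 131I is true disease. For lesions seen only on PSMA, "the lesions will be characterized as either true or false positives in comparison to the appearance of the lesion on conventional imaging" (ultrasound, CT or MRI, by consensus reading). Totals per technique are then compared, the data feed sensitivity and specificity, and a larger PSMA total is described as promising support for a bigger trial.

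**Imaging at the PSMA visit.** Section 5.1 says "A neck MRI with gadolinium (MR) will be performed at the time of the PET imaging". Section 5.1.2.1 adds a whole-body MRI for attenuation correction and localization.

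**The concern.** When two scans are up to 360 days apart, a lesion seen on only one of them has three possible explanations: the other tracer missed it, it was not there yet, or it had gone. Section 6.10 allows only the first, apart from a false-positive call on an unconfirmed PSMA-only lesion. Nothing restricts or analyses the interval within the 360 days, fixes the date of the conventional imaging, or deals with progression or treatment between scans.

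Secondary objective 2 compares the sensitivities, and the closing statement on lesion numbers in 6.10 is what would be cited to justify a larger trial. The background in section 1 points to aggressive, radioiodine-refractory disease, where new lesions within a year are plausible. An apparent advantage or disadvantage of PSMA could then partly reflect elapsed time.

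**Working it through.** **1. The plan's own figure.** Section 6.8 gives 20 patients per comparator, sensitivity 0.90 against 0.65, one-sided 0.05, power 0.87. An exact binomial test against a fixed 0.65, rejecting at 17 or more of 20, has alpha 0.044 and power 0.867, so the figure reproduces. It treats the comparator as a constant. The analysis in 6.10 uses observed comparator lesions, which are exposed to the time lag.

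**2. Where each kind of lesion goes under 6.10.**

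| Lesion | Scored as |
|---|---|
| Arose after the comparator scan, PSMA-positive, confirmed | PSMA true positive; by implication a comparator miss |
| Same, not confirmed | PSMA false positive, though 6.10 does not expressly remove it from the raw count |
| Comparator-positive, gone before PSMA | True disease; PSMA miss |

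The comparator miss is not stated in words. It follows from comparing both sensitivities against this reference.

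**3. Effect of new lesions on the sensitivity gap.** Inputs: comparator sensitivity 0.65 (section 6.8). Assumptions: PSMA also 0.65, so the true difference is zero; independent misses; new lesions equal to a fraction g of the old ones; a share c of PSMA-only lesions confirmed; no lost lesions. Per 100 old lesions:

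- comparator-positive: 65, of which PSMA-positive 0.65 × 65 = 42.25
- PSMA-only, old, confirmed: 0.65 × 35 × c = 22.75c
- PSMA-only, new, confirmed: 65gc
- reference total: 65 + 22.75c + 65gc
- recorded gap (PSMA minus comparator) = (22.75c − 22.75 + 65gc) / (65 + 22.75c + 65gc)

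Example, c = 1 and g = 0.2: 13 / 100.75 = 0.129 (PSMA 0.774, comparator 0.645).

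| Confirmed share c | g = 0 | 10% | 20% | 30% | Shift from g = 0 |
|---|---|---|---|---|---|
| 100% | 0.0 | +6.9 | +12.9 | +18.2 | about 7/13/18 points |
| 70% | −8.4 | −2.7 | +2.5 | +7.2 | about 6/11/16 points |

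The negative starting value at 70% arises because comparator positives are true automatically while PSMA-only lesions need confirmation.

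**4. Effect of lost lesions.** If a fraction l of old lesions has gone by the PSMA date and c = 1, the numerator becomes 65(1 − l) + 65g − 65 = 65(g − l). A 10% loss cancels 10% new lesions exactly, and 20% cancels 20%.

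**5. Lesion count.** Simulation assumptions: 40 patients; 1 + Poisson(2) lesions each (mean 3); beta-binomial detection with mean 0.65 for both tracers and within-patient correlation 0.3; no confirmation step and no five-lesion cap. Patients are kept only if at least one lesion is comparator-positive, to reflect criterion 2. The chance that PSMA shows more lesions in total:

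| Lost lesions | g = 0 | 10% | 20% | 30% |
|---|---|---|---|---|
| none | about 10% | about 35% | about 67% | about 87% |
| 10% | – | about 12% | about 36% | about 66% |

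Without the entry requirement and with no lost lesions, the figures are 48/75/91/97%, but those do not describe this protocol.

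**The case against.** A reader might infer that progression always favours PSMA, or that any PSMA gain is merely elapsed time. The documents do not support either, for four reasons.

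- **Confirmation is not assured.** The gadolinium MRI covers the neck. The whole-body MRI is for attenuation correction and localization, so a new distant lesion may not be confirmed and would then count against PSMA as a false positive. The same could happen if the conventional imaging is as old as the comparator.
- **Loss works the other way.** Treated or resolved lesions are charged to PSMA and can cancel the effect entirely (step 4).
- **Other features favour the comparator.** Criterion 2 admits only patients with comparator uptake, and the reference accepts comparator positives without confirmation. At 50% confirmation the recorded gap is −10.2/−5.9/−1.9 points for 10/20/30% new lesions, so PSMA never looks better. The results in step 3 leave out entry selection.
- **The status of the count.** This is a feasibility pilot. The statement on larger numbers is not a decision threshold, and the limit in section 6.7 to the five largest lesions may drop small new ones.

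All four stand and limit the size and certainty of the bias. None supplies the missing date rule. Opposing biases of unknown size cannot be assumed to cancel, and a pilot's lesion comparison is what the next trial would rest on.

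**Conclusion.** The point holds as a gap in the analysis plan that should be fixed. As written, 6.10 counts a confirmed lesion that arose after the comparator scan as a PSMA success and a comparator miss, and counts a lesion that went away before PSMA as a PSMA miss. Each error has a clear direction. Their net does not, because the documents give no rate of new or lost lesions.

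The illustrative shifts of 6 to 18 points rest on assumed equal sensitivities of 0.65, independent misses, no lost lesions, 70 to 100% confirmation and 10 to 30% new lesions. The rise in the chance of a larger PSMA count, from about 10% to about 35/67/87%, rests on the simulation assumptions in step 5, again with no losses. These figures show that the lag can matter. They do not estimate the bias in this trial.

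**What to change.** Amend section 6.10 as follows.

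1. Record for each patient the interval from comparator to PSMA scan and any therapy in between. State whether the optional second PSMA scan is excluded from the comparison.
2. Using existing imaging from around the comparator date, label each confirmed PSMA-only lesion as present then, new, or undatable.
3. Using the PSMA-visit MRI, label each comparator-only lesion as still present, resolved, or undeterminable.
4. Do not count lesions shown to be new as comparator misses, or lesions shown to have resolved as PSMA misses.
5. Keep undatable and undeterminable lesions in the analysis. Report bounds treating them all one way and then the other, for both the sensitivity comparison and the lesion count. Dropping only undatable PSMA-only lesions would be one-sided: it would remove genuine comparator misses while resolved lesions were still charged to PSMA.
6. Add a sensitivity analysis in patients scanned within a prespecified short interval, for example 90 days. That cut-off is an assumption; the documents give none.

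The cost is SAP wording and re-reading of existing scans, with no new imaging or patients. The stated uncertainty will widen, mainly for radioiodine patients without CT from that time, and the stated PSMA gain may shrink.

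### The 0.87 power in section 6.8 fits a one-sample test against a fixed 0.65, not the described comparison with FDG or 131I as measured here; and section 6.10 defines no true negative, so specificity cannot be compared as written

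*Combined protocol and SAP*

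**What the plan says.** - **Entry.** Section 3.3.1, criterion 2, requires a whole-body FDG PET/CT, I-123 or I-131 scan within 360 days of the scheduled "PSMA PET demonstrating uptake".
- **Objective.** Secondary objective 2 (section 2.2) reads "To determine and compare the sensitivity and specificity of" PSMA PET against FDG PET and/or radioiodine scintigraphy.
- **Sample size.** Section 6.8 assumes that half the patients have 131I and half have FDG. It takes sensitivity as 0.65 for each comparator and 0.90 for PSMA PET. It gives 20 patients per comparison at one-sided 0.05 and power 0.87, 40 in total. It says the sensitivities will be compared but names no test.
- **Reference standard.** In section 6.10, presence of a lesion on 131I or FDG "will be considered true positive disease". "The gold standard for an individual lesion will be FDG or" 131I, when the lesion is "positive on either imaging study". For lesions on neither scan, "then consensus reading of conventional imaging will be performed to determine true and" false positives.
- **Analysis.** Section 6.10 counts lesions by technique and adds that "this data will be used to determine the sensitivity and specificity of" PSMA-11.

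**The concern.** The 0.65 versus 0.90 contrast is the only powered hypothesis in the plan and the stated basis for 40 patients. Two features of the plan pull against it. Patients enter because a comparator scan was positive, and that same scan then serves as the reference. A comparator chosen for being positive cannot show the assumed 35% miss rate per patient when each patient has only one comparator. The analysis section meanwhile works in lesions, for which no sample size was calculated. If 0.87 is read as the power to show PSMA better than FDG or 131I, readers will expect a conclusion that the data cannot carry. The specificity half of secondary objective 2 has a separate problem: specificity needs negatives, and the plan sorts extra lesions only into true and false positives.

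**Working it through.** **Inputs.** From section 6.8: n=20 per comparison, comparator sensitivity 0.65, PSMA sensitivity 0.90, one-sided alpha 0.05, stated power 0.87. I work with the sensitivities. Section 6.8 writes the null as 65% misclassification, whereas a sensitivity of 0.65 implies 35%; 35% against 10% gives the same result as below, while a literal 65% against 10% gives power above 0.999.

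**1. Reproducing 0.87.** Let X be the number of PSMA-positive patients among 20, X ~ Binomial(20, p), tested against a fixed p = 0.65.
- P(X ≥ 16 | 0.65) = 0.118, above 0.05.
- P(X ≥ 17 | 0.65) = 0.0444, so the test rejects at 17/20 or more.
- P(X ≥ 17 | 0.90) = 0.867, which rounds to the stated 0.87.
- The one-sample normal approximation, Φ[(0.25 − 1.645·√(0.65·0.35/20)) / √(0.90·0.10/20)], also gives 0.867.

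Section 6.8 names no test, so the one-sample design is inferred from this match.

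**2. Power when the comparator is measured, granting it a sensitivity of 0.65** (n=20, one-sided 0.05).
- Two independent proportions with pooled z, mean proportion 0.775: Φ[(0.25 − 1.645·√(2·0.775·0.225/20)) / √((0.65·0.35 + 0.90·0.10)/20)] = 0.60.
- Exact paired (McNemar) test. Let c be the proportion positive on the comparator only; the proportion positive on PSMA only is then 0.25 + c. The documents do not give c, so a range is shown:

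| Assumed c | Power |
|---|---|
| 0 | 0.59 |
| 0.065 (independent detection, 0.65 × 0.10) | 0.42 |
| 0.10 (the maximum, since PSMA misses 10%) | 0.37 |

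**3. What entry does per patient.** With one comparator per patient, and entry uptake read as a lesion, every patient is comparator-positive and that lesion is true by the section 6.10 rule. Comparator sensitivity is 20/20, against the 13/20 implied by 0.65. No patient can be PSMA-positive and comparator-negative, so a paired test for PSMA superiority has power 0 at n=20 and at n=40. The best PSMA result is a tie at 20/20. For a single tracer to show 13/20, 20 − 13 = 7 patients in that group would need both scans, negative on that tracer and positive on the other.

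**4. Per lesion.** Confirmed PSMA-only lesions count as disease the comparator missed, so comparator sensitivity can fall below 100%. Section 6.8 gives no number of lesions and no within-patient correlation, so its power does not apply to that analysis. The limit of five lesions per study in section 6.7 reduces clustering but does not remove it.

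**5. Specificity.** Specificity = TN/(TN + FP). Section 6.10 yields TP and FP for PSMA and defines no TN at lesion, region or patient level. For PSMA the ratio is 0 or undefined. A comparator-positive lesion cannot be false under the rule, so with FP = 0 and no TN the comparator's ratio is 0/0.

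**6. What 40 patients can support.** Exact (Clopper-Pearson) 95% intervals for agreement with the entry scan, taking 90% as an example: 18/20 gives 68% to 99%; 36/40 gives 76% to 97%.

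**The case against.** The other side has four good arguments.

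- **The one-sample test can be run.** Section 6.8 writes its hypotheses against a constant, which fits that design. A reader might infer that 0.87 matches no comparison the study can make; that goes too far. Twenty patients can be tested against 0.65. The test would, however, set agreement with the entry scan against an outside constant, which is not the comparison with FDG or 131I that section 6.8 describes.
- **The written analysis is per lesion.** This stands. The 20/20 result is a per-patient statement and should not be carried over to lesions. It does not rescue the 0.87, which counts patients.
- **The 100% is conditional.** One comparator per patient is a planning assumption. Section 2.2 allows both scans and mentions radioiodine-negative cancers, so a patient entered on FDG could be negative on radioiodine. Criterion 2 asks for uptake, not explicitly a lesion read as tumor. I-123 permits entry, but the section 6.10 reference names only FDG and 131I. These limits are accepted.
- **This is a feasibility study, and the comparison is secondary.** True, and section 6.10 seeks only preliminary evidence. Section 6.8 still rests n=40 on this hypothesis.

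Three other stronger readings also fail. Comparator specificity is not 100% by rule; without true negatives it is undefined. A tie at best does not mean PSMA would be shown worse: at 0.90 sensitivity, a significant paired loss needs at least 5 misses in 20, with probability 0.043. And although comparator lesions are accepted unchecked while PSMA-only lesions need confirmation on "conventional imaging (thyroid ultrasound, CT and MRI"), the documents fix neither the size nor the direction of any bias. That asymmetry is a limitation to disclose.

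**Conclusion.** The point holds in this form. The 0.87 is, by inference, the power of a one-sample test of PSMA against a fixed 0.65. It should not stand as the power of a comparison with FDG or 131I measured in this study, which at n=20 would be about 0.60 (two-sample) or 0.37 to 0.59 (paired) even at the assumed sensitivities. Per patient, with one comparator each and entry uptake read as a lesion, the assumed 0.65 cannot occur and PSMA superiority cannot be shown. Patients with both scans, or entered on I-123, fall outside that strict statement. Per lesion, sensitivity can be computed, but no power has been calculated for it. The specificity comparison in secondary objective 2 cannot be computed as written; that conclusion needs none of these assumptions. The plan should be corrected on both counts. Feasibility of the imaging itself is not in question.

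**What to change.** 1. **Section 6.8.** Stop presenting 0.87 as the power of a comparison with FDG or 131I. State that entry selects comparator-positive patients. Justify n=40 by the precision of PSMA's per-patient agreement with the entry scan, for example with the intervals for 18/20 and 36/40 shown in the working.
2. **Sections 2.2 and 6.10.** Report PSMA's per cent agreement with comparator-positive lesions and the number of confirmed PSMA-only lesions, with intervals that treat the patient as the cluster (for example a bootstrap that resamples patients). Do not present these as an unbiased sensitivity comparison. Disclose that the lesion reference treats the two techniques differently.
3. **Specificity.** Replace the comparison with PSMA positive predictive value under the section 6.10 reference and the number of unconfirmed PSMA foci per patient. Carry the change into secondary objective 2 in the Abstract as well.

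The cost is wording, with no added scans or patients. The real loss is the powered sensitivity contrast and the specificity claim: n=40 would rest on precision instead of power.
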